# 1.2 Study design

MG0020 is a Phase 3, open-label, randomized, 2-period, 2-sequence crossover study planned to be conducted at multiple sites in Europe, Japan, and North America. In MG0020, the safe and effective self-administration of rozanolixizumab using the syringe driver and manual push administration methods by study participants with gMG will be evaluated using a crossover design over (Figure 1–1).

Study participants in Europe and North America are proposed to receive fixed doses of rozanolixizumab for statements as described below:

- Body weight  $\geq$ 35kg to <50kg: dose to be administered
- Body weight ≥50kg: dose to be administered

Study participants in Japan are proposed to receive fixed unit doses of rozanolixizumab across body weight tiers for statements as described below:

- Body weight ≥35kg to <50kg: dose to be administered
- Body weight  $\geq$  50kg to <70kg: dose to be administered
- Body weight ≥70kg to <100kg: dose to be administered
- Body weight ≥100kg: dose to be administered

Rozanolixizumab-naïve study participants and study participants previously exposed to rozanolixizumab will be included in the study.

Approximately 40 participants will be screened to achieve approximately 30 randomly assigned and evaluable participants for an estimated total of 15 evaluable participants per sequence. See Section 5 for the determination of sample size.

The total duration for each study participant is up to 29 weeks, including a Screening Period of up to 4 weeks, an Treatment Period, and an up to 7-week Safety Follow-up Period (ie, End of Study Visit is 8 weeks after the last dose of rozanolixizumab in the Treatment Period, or earlier, if the study participant moves on to a post-trial access program or to commercially available rozanolixizumab during the Safety Follow-up Period).

Stion Treatment Period of MG0020 starts with standardized trainings over the The Training Period when the study participant is trained on both the manual push course of a and the syringe driver administration methods. During the Training Period, the study participant will receive doses of rozanolixizumab SC and should practice both methods of administration at the study site. To act as a reference for the preference question (HCP vs selfadministration) and to demonstrate subcutaneous infusions of rozanolixizumab, the first administration will be imperatively performed by the HCP. For all remaining training visits, the study participant should perform as many self-administrations as possible (under HCP supervision) depending on their training status. Self-administration under HCP supervision or administration by HCP will be documented in the case report form (CRF). At Visit 8 ( ), after the completion of the Training Period and following the investigator's confirmation of the eligibility to perform self-administration, the study participant will be randomized 1:1 to either the syringe driver or to the manual push administration method. After completing Selfadministration Period 1 (at Visit 13 []]), the study participant will crossover to the alternative administration method, entering Self-administration Period 2 (Visit 14 ]). A final release of the study participant for home self-administration will be based on a successful demonstration of self-administration using the assigned mode of administration (manual push or syringe driver use) at Visit 9 (manual and Visit 15 (manual), respectively. Study participants who cannot be confirmed eligible for self-administration will not perform self-administration and can continue to be treated on-site per protocol based on investigator decision. Additionally, if a study participant becomes no longer eligible for self-administration during the Selfadministration Periods, he/she can continue to be treated on-site per protocol based on investigator decision. Adverse events, concomitant medication, vital signs, ECG, suicidality, blood and urine samples for safety laboratory tests, pregnancy tests and IgG will continue to be collected from these study participants until End of Study Visit/Early Withdrawal Visit.

[figure not shown]
During both Self-administration Period 1 and Self-administration Period 2, self-administration will be performed at the site for 3 visits and at home (ie, unsupervised/not in the presence of an HCP) for 3 consecutive visits.

After the Self-administration Periods, study participants will enter the 7-week Safety Follow-up Period.

Following participation in MG0020, study participants who have completed the study (End of Study Visit performed) will have the option of a post-trial access to rozanolixizumab, if available according to local guidance, or to commercially available rozanolixizumab, at the discretion of the investigator.

The schedule of activities can be found in the protocol. The infusions are planned from Visit 2 (for the Visit 7 (for the Training Period, from Visit 8 (for the Visit 13 (for the Self-administration Period 1 and from Visit 14 for the Visit 19 (for the Self-administration Period 2.

## Figure 1–1: Study Schema

# 2 STATISTICAL HYPOTHESES

This is an estimation study design with no formal statistical hypothesis testing.

## 2.1 Multiplicity adjustment

As there is no statistical hypothesis testing in this study, there will be no account for multiplicity.

# 3 POPULATIONS FOR ANALYSIS

- Enrolled Set (ES): All study participants who have signed the informed consent form.
- Safety Set (SS): All study participants who received at least 1 dose of investigational medicinal product (IMP) (partial or full). Analysis of this set will be according to the administration method the participants actually used and will be used for analyses of safety and demography outcomes as required.
- Randomized Safety Set (RSS): All participants who are included in SS and were randomized. Analysis of this set will be according to the administration method the participants actually used and will be used for analyses of safety, demography, and efficacy/outcomes.
- Full Analysis Set (FAS): All participants who are included in SS, were randomized and completed both Self-administration Periods. Both Self-administration Periods will be considered as complete if self-administration occurred on Visits 13 and 19 in accordance with the randomization scheme.

#### STATISTICAL ANALYSES 4

#### 4.1 General considerations

Statistical analysis and generation of tables, figures, participant data listings, and statistical output will be performed using SAS Version 9.4 or higher. All tables and listings will use Courier New font size 9.

Zation Descriptive statistics will be displayed to provide an overview of the study results. For categorical parameters, the number and percentage of participants in each category will be presented. The denominator for percentages will be based on the number of participants appropriate for the purpose of analysis. Unless otherwise noted, all percentages will be displayed to 1 decimal place. No percentage will be displayed for zero counts, and no decimal will be presented when the percentage is 100%. For continuous parameters, descriptive statistics will include number of participants with available measurements (n), mean, standard deviation (SD), median, minimum, and maximum. If not otherwise specified, summary statistics will be displayed by sequence and overall for demographics, and by period and by self-administration method for period-specific assessments.

Decimal places for descriptive statistics will always apply the following rules:

- "n" will be an integer.
- Mean, SD, and median will use 1 additional decimal place compared to the original data.
- Minimum and maximum will have the same number of decimal places as the original value.

The Baseline value is defined as the last nonmissing measurement before the first administration (prior to the Training Visits) at Visit 2 ( if not otherwise specified. Scheduled or unscheduled measurements can be used as the Baseline value.

In case of missing visit information for Myasthenia Gravis Activities of Daily Living (MG-ADL) and Self-Injection Assessment Questionnaire (SIAQ) data, visit windowing will be applied based on the Protocol Schedule of Activities (Section 1.3). Otherwise, visit windows will not be used.

A complete set of data listings containing all documented data and all calculated data (eg, change from Baseline) will be generated. They will be ordered by sequence, participant number, period, and timepoints as applicable.

#### 4.1.1 Analysis time points

#### Relative day for listings 4.1.1.1

Relative day will be calculated depending on the position of the day compared to first and last doses of study drug:

For days on or after the day of first dose of study drug and prior to or on the day of last study drug dose:

Relative Day = [(Event Date – Date of First Dose)+1]

The day of first dose will be Day 1.

For days prior to the first dose of study drug:

Relative Day = [(Event Date – Date of First Dose)]

The day prior to first dose will be Day -1.

For days after the last dose of study drug:

Relative Day = + [(Event Date – Date of Last Infusion)]

The day after the last dose will be Day + 1.

Relative day will not be calculated for partial dates.

#### 4.1.1.2 Analysis periods

The following study periods are defined for the classification by study period:

- Screening Phase: Prior to the date of first dose of study drug
- **Treatment Phase:**
- authorization eff-Training Period: From the first dose (Visit 2) of study drug to the first dose in Sel administration Period 1 (Visit 8) minus one day
  - Self-administration Period 1: Starts one day after the end of Training Period and ends with the first dose in Self-administration Period 2 (Visit 14) minus one day
  - Self-administration Period 2: Starts one day after the end of Self-administration Period 1 and ends at the end of Visit 20 assessments (EOT date).
- Follow-up Phase: Starts one day after the end of Self-administration Period 2 and ends after • the safety follow up assessments of Visit 21.

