8.3.1 Time period and frequency for collecting AE and SAE information

All AEs and SAEs will be collected from the signing of the ICF until the End of Study Visit (Visit 21) at the time points specified in the Schedule of Activities (Section 1.3).

All TEAEs occurring from the first administration of rozanolixizumab during the Training Period up to the first administration of rozanolixizumab in Self-administration Period 1 will be considered treatment-emergent in the Training Period.

All TEAEs occurring during Self-administration Period 1 up to the first administration of rozanolixizumab in Self-administration Period 2 will be considered treatment-emergent in Self-administration Period 1.

All TEAEs occurring during Self-administration Period 2 up to 8 weeks after the last administration of rozanolixizumab will be considered treatment-emergent in Self-administration Period 2.

Local site reaction AEs will be considered treatment-emergent up to 24 hours after each administration during the Training Period and Self-administration Periods.

In order to ensure complete safety data collection, all AEs occurring during the study (ie, after the signing of the ICF), including any pretreatment and posttreatment periods required by the protocol, must be reported in the CRF even if no study medication was taken but specific study procedures were conducted. This includes all AEs not present before the initial visit and all AEs that recurred or worsened after the initial visit.

All SAEs will be recorded and reported to the sponsor or designee within 24 hours, as indicated in Appendix 3 (Section 10.3). The investigator will submit any updated SAE data to the sponsor within 24 hours of it being available.

The investigator is specifically requested to collect and report to UCB (or its representative) any SAEs (even if the investigator is certain that they are in no way associated with the study medication), up to 30 days from the end of the study for each participant, and to also inform participants of the need to inform the investigator of any SAE within this period. Serious AEs that the investigator thinks may be associated with the study medication must be reported to UCB regardless of the time between the event and the end of the study.

The method of recording, evaluating, and assessing causality of AE and SAE and the procedures for completing and transmitting SAE reports are provided in Appendix 3 (Section 10.3).

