#### 4.3 Secondary endpoints analysis

#### 4.3.1 Secondary endpoints

#### 4.3.1.1 Definition of endpoint(s)

The secondary endpoints are:

- Occurrence of TEAEs after syringe driver or manual push self-administration from Visit 2 up to the End of Study Visit (Visit 21 [Week 26]).
- Occurrence of local site reactions up to 24 hours after each administration during the Training Period and Self-administration Periods.
- Occurrence of medication errors associated with adverse reactions during the 2 Selfadministration Periods of the study.)

A TEAE is defined as an AE starting on or after the date of first administration of rozanolixizumab in the study, up to and including 8 weeks (56 days) after the final dose.

A TEAE will be assigned to the Training period if the start date of the event is on or after the date of the first administration of rozanolixizumab during the Training Period and before the date of first administration of rozanolixizumab in Self-administration Period 1.

A TEAE will be assigned to the Self-administration Period 1 if the start date of the event is on or after the date of the first administration of rozanolixizumab in Self-administration Period 1 and before the date of the first administration of rozanolixizumab in Self-administration Period 2.

A TEAE will be assigned to the Self-administration Period 2 if the start date of the event is on or after the date of the first administration of rozanolixizumab in Self-administration Period 2 and up to the end of Visit 20 assessments (EOT date).

Where dates are missing or partially missing, AEs will be assumed to be treatment-emergent unless evidence exists that does not allow the AE to be treatment-emergent. Handling of missing dates for classification of AEs as TEAEs is described in Section 4.1.8.

The local site reactions up to 24 hours after each administration are defined as AEs reported as local site reactions as per CRF within one day after rozanolixizumab administration.

Medication errors associated with adverse reactions are defined as the AEs whose preferred terms belong to the Standardised MedDRA Queries (SMQ) "Medication errors" and leading to adverse reactions.

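### Adverse events of early leavers stay in Training or Period 1 for up to 56 days off drug, while Period 2 is closed at Visit 20

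*SAP*

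**What the plan says.** SAP 4.1.1.2 bounds the first two periods by the arrival of the next one. Training ends the day before the first Period 1 dose (Visit 8), and Period 1 "ends with the first dose in Self-administration Period 2 (Visit 14) minus one day". Period 2 has a boundary of its own: it "ends at the end of Visit 20 assessments (EOT date"). The Follow-up Phase "Starts one day after the end of Self-administration Period 2".

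SAP 4.3.1.1 applies the same bounds to TEAEs. The overall limit is "up to and including 8 weeks (56 days) after the final dose". Period 1 takes events with onset "before the date of the first administration of rozanolixizumab in Self-administration Period 2", whereas Period 2 takes them only "up to the end of Visit 20 assessments (EOT date"). SAP 4.5.3.1.1 (laboratory) and 4.5.3.2 (vital signs) repeat these rules, also with a 56-day limit after the last infusion.

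Two other rules bear on this. SAP 4.1.3 maps assessments made at the Early Withdrawal visit but says nothing about adverse event onset dates. SAP 4.1.8 places each TEAE in exactly one period unless doubt about the dates remains.

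Protocol 8.3.1 has the same open-ended rules for Training and Period 1, but its Period 2 rule is longer: "All TEAEs occurring during Self-administration Period 2 up to 8 weeks after the last" administration. The SAP version history records the shortened Period 2. SAP 4.8, which lists departures from the protocol, does not.

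**The concern.** A participant who stops study drug in Training or Period 1 never receives the dose that would close the period, and no Follow-up Phase ever starts for that person. The only limit left is the TEAE definition. These participants are followed: protocol 7.1.3 sends them to an Early Withdrawal Visit and then Safety Follow-up, and 7.2 asks for an End of Study Visit except after withdrawal of consent. Off-drug events will therefore be collected and must be placed somewhere.

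The result is inconsistent attribution. An event 30 days after the last dose counts under the assigned method if the participant left in Period 1, but falls outside Period 2 if the participant completed it. The outputs concerned are the Training TEAE table (Safety Set) and the by-period and by-method adverse event, laboratory and vital-sign tables. In these, about six weeks of mainly on-drug time in completers would be mixed with up to eight off-drug weeks in leavers.

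**Working it through.** **1. Visit calendar.** Visit days are blacked out, so I rebuilt them from weekly visits with Visit 2 as Day 1: day of Visit v = 1 + 7(v − 2).

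- This gives Visit 7 = 36, Visit 8 = 43, Visit 13 = 78, Visit 14 = 85, Visit 19 = 120 and Visit 20 = 127.
- Days 36, 78 and 120 match the exposure categories in SAP 4.5.1.
- Day 43 matches the vital-sign footnote to protocol Table 1-3, read with SAP 4.5.3.2 (Visit 8).
- Visit 20 falls in week (127 − 1)/7 + 1 = 19, as in the SAP version history.
- The End of Study Visit is 120 + 56 = Day 176, week (176 − 1)/7 + 1 = 26, as in SAP 4.3.1.1.
- The plan's own limit reproduces: 8 × 7 = 56 days. Visit 20 is 127 − 120 = 7 days after the last dose. This agrees with protocol 4.1, where End of Study is 8 weeks after the last dose and follow-up lasts up to 7 weeks.

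**2. Completers.** Training: 43 − 1 = 42 days. Period 1: 85 − 43 = 42 days. Period 2: 127 − 85 + 1 = 43 days. These are essentially equal.

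**3. Early leavers.** The k-th weekly infusion falls on period day 7(k − 1) + 1. Adding 56 gives the window as written in Training or Period 1. Adding 7 gives the Period 2 window, assuming that the Early Withdrawal visit counts as the EOT date (the schedule gives them one column) and falls 7 days after the last dose.

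| Last infusion in period | Training or Period 1 | Period 2 | Ratio |
|---|---|---|---|
| 1st | 1 + 56 = 57 days | 1 + 7 = 8 days | 7.1 |
| 3rd | 15 + 56 = 71 days | 15 + 7 = 22 days | 3.2 |
| 6th | 36 + 56 = 92 days | 36 + 7 = 43 days | 2.1 |

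**4. Illustration of size.** Neither a TEAE rate nor a dropout rate is given. Assume a constant hazard and a TEAE incidence p of 30% to 50% per 42 days, so λ = −ln(1 − p)/42, and incidence over w days is 1 − exp(−λw). Take a leaver whose last dose is the third.

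| p | 22 days | 71 days | Difference |
|---|---|---|---|
| 30% | 17% | 45% | 28 points |
| 40% | 23% | 58% | 34 points |
| 50% | 30% | 69% | 39 points |

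The shift in the Period 1 proportion is the leaver share times the difference. At 3% leaving it is 0.03 × 28 to 0.03 × 39, or 0.8 to 1.2 points. At 10% it is 2.8 to 3.9 points. With 30 participants, 10% is three leavers, and the excess is 3 × 0.28 to 3 × 0.39, or about one extra participant counted with a TEAE.

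**The case against.** The strongest reply is SAP 4.1.7. It makes stopping self-administration during the Self-administration Periods an intercurrent event and leaves later data out of the primary and secondary endpoints that focus on self-administration. Its context is participants who carry on with on-site dosing, but someone who stops drug in Period 1 has also stopped self-administering. On that reading their late TEAEs are already out of the by-method secondary endpoint. This stands as a limit on the concern. It does not reach Training, which lies outside those periods, or the general safety tables, where 4.1.7 deliberately keeps all later data. Nothing links 4.1.7 to the assignment rules in 4.3.1.1.

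A second reply is that the SAP follows protocol 8.3.1 for Training and Period 1, and that the asymmetry for leavers arises only from cutting Period 2 at Visit 20. That is correct. But restoring the protocol rule would give completers a Period 2 window of 176 − 85 + 1 = 92 days against 42 in Period 1, a larger imbalance affecting more people.

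A reader might infer that the syringe driver versus manual push comparison as a whole is biased. The documents do not support that. Each method occurs in both periods, so the overall method columns diverge only if Period 1 dropout differs by method. There is no hypothesis test, and local site reactions have a one-day window and are untouched. Nor are participants who lose self-administration eligibility but continue on-site dosing early leavers: they still receive doses on the Period 2 schedule.

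Finally, the size is assumed. A constant hazard carries the on-drug rate through 56 days off drug, which probably overstates it.

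**Conclusion.** The concern holds in a limited form. The SAP's stated rules attribute off-drug events of early leavers to Training or Period 1 for up to 56 days, against about 7 days in Period 2, and no other rule in the plan corrects this for adverse event onset dates.

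Only participants who stop drug before the next period's first dose are affected. The Training table and the general by-period and by-method safety tables are exposed. The by-method secondary endpoint is exposed only if 4.1.7 is not read to exclude data after self-administration stops. The 71 versus 22 day contrast depends on the rebuilt weekly calendar and on an Early Withdrawal visit 7 days after the last dose; the documents state no such interval. The shift of about 1 to 4 points in the Period 1 proportion is illustrative and probably an upper range. It is worth correcting before the tables are produced, but it does not undermine the study's conclusions.

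**What to change.** In SAP 4.1.1.2, 4.3.1.1, 4.5.3.1.1 and 4.5.3.2:

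- End Training and each Self-administration Period at the earlier of the day before the next period's first dose and the EOT/Early Withdrawal visit date. State a fallback where there is no such visit, for example last infusion + 7 days, to match Visit 20.
- Start the Follow-up Phase the next day for every participant and show later TEAEs there, so that none are lost. Include a Safety Set column: randomization is at Visit 8, so Training leavers are not in the Randomized Safety Set.
- State how these bounds work with 4.1.7, in particular whether TEAEs after stopping drug enter the by-method secondary endpoint.
- List the departure from protocol 8.3.1, including the Period 2 cut at Visit 20, in Section 4.8.

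The cost is SAP wording and one date derivation, with no new data. The downside is that leavers' late events move from a method column to Follow-up. Windows will still differ in length between leavers and completers because leavers have less time on drug; the change makes the post-dose tail follow one rule in every period.

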#### Definition of baseline values 4.1.2

The Baseline value is defined as the last nonmissing measurement before the first administration of IMP (prior to the Training Visits) at Visit 2 ( if not otherwise specified.

#### Mapping of assessments performed at Early Withdrawal Visit 4.1.3

Efficacy and safety assessments at Early Withdrawal (EW) will be assigned to the next scheduled visit (following the last scheduled visit that the study participant completed prior to withdrawal) where each assessment is evaluated as per protocol. This approach means that there is a chance that EW data will be mapped to different visits according to the schedule of assessments. If the mapped visit is the first visit in the next period, the visit will be assigned to the previous period.

